Research Protocol

Title: Investigation of the effect of environmental temperatures on non-contact thermal imaging for core body temperature measurement

Principal Investigator: [name]

Co-Investigators: [name] PhD, [name] PhD, [name]

A. Introduction

The purpose of this study is to examine the effect of the local environment and the physiology of the human body on the relationship between core body temperature and inner canthus (region near tear duct) skin temperature measured using non-contact thermal imaging. The overall goal of this research study is to validate and improve the science of non-contact core body temperature measurement. The present inquiry is of minimal or no risk, is not focused on a vulnerable population, will include study participants who are not current members of the St. Olaf community and findings will be shared outside St. Olaf, thus this is a Type 2 project.

Core body temperature is one of the vital signs, being used to diagnose conditions associated with abnormally high or low temperatures. Normal body temperature can vary with gender, recent activity, food and fluid consumption, mental and physical stress, time of day, and, in women, the stage of the menstrual cycle¹. Clinical studies of oral temperatures acquired using thermometers having a measurement accuracy of 0.1C (0.18F) in healthy adult humans have found a distribution with a standard deviation of approximately 1F (0.6C) and averages ranging from 97.9F to 98.6F². Oral thermometry is sensitive to probe placement, recent speaking or mouth-breathing, recent fluid or food consumption and even air temperature. In-ear thermometry is an oft-used alternative but is affected by ear geometry and debris, often requiring re-measurement attempts. These thermometry methods can be inconvenient in some clinical practices due to the time required, and thus, non-contact or other surface-based thermometry methods are desired.

The use of non-contact core temperature screening has become widespread in society due to the COVID-19 pandemic. Past clinical trials have demonstrated the sensitivity and accuracy of thermographic (image-based) non-contact body temperature measurement. A comprehensive

¹ Normal physiologic variability in core temperature is well established, with the time-of-day and menstrual cycle generally accepted as contributing the largest sources of variability, each ranging from 0.3 to 1F in magnitude.

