The number of samples required to understand the impact of environmental or physiological confounds on surface temperature is dependent on the variability in the core-to-surface temperature physiologic offset. The variability in core body temperature has been found to be close to 1F but note the research design proposed here is not dependent on normal person-to-person variability in core temperature because the temperatures obtained are all referenced to each individual's core temperature. To estimate the likely physiologic variability in the population, we can extrapolate based on surface temperature data taken by the primary thermographic system obtained over the past six months because this should be approximately the vector sum of variability in core temperature, measurement accuracy, and the physiologic variability. This data must be interpreted with caution, because these have been obtained with less control over environmental conditions and furthermore we do not know the core body temperature variability in the preliminary data population, but it can provide a reasonable error bound. This data shows a standard deviation of 1.11F (note, this value is obtained without *any* bias-to-normal algorithm, which appears to be a novel feature in this research), which would suggest the physiologic variability component is at most 0.48F, or half a degree. Therefore, in order to determine the sensitivity and specificity at detecting elevated temperatures of 1.8F (100.4F threshold) to within 20% (meaning, can we significantly distinguish 100.40 from 100.04F with the aforementioned standard deviation in a one-sided paired t-test), we require 28 participants. To account for possible data collection failures, we intend to recruit as many as 45 participants.

Data Collection

- Demographic and clinical data: minimal demographic and clinical data will be collected by interview with the participant at the time of the imaging studies including age, gender, any disease- or autonomic-modulating treatment, height, weight and any antipyretic medications in past 12 hours in order to allow adjustment for confounding factors. We do not intend to collect data on menstrual cycle due to the additional potential privacy concerns this will place on participants worried about this data which is significantly more sensitive than other data being collected.

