The rooms will each consist of a portable tent with dimensions of at least 5x5ft base and height of 6ft. The critical requirement of said tent is sufficient thermal isolation from ambient temperatures to allow the maintenance of the required elevated or cooled temperature setpoints to within 1.8F. At present time, the most suitable tent is the THUNDERBAY Ice Cube 3 Man Portable Ice Shelter <https://www.amazon.com/gp/product/B019CU59VI>. This tent is surprisingly large, and has sufficient space to allow four adults to stand with 2 feet between adjacent people or two people with over 3 feet between them. The thermal radiant intensity of the walls of this tent do not match that of the elevated or cooled air temperature, because these walls directly contact and conduct to the ambient air and equilibrate between the ambient and internal temperatures, thus they radiate closer to the ambient temperature. Therefore, additional radiating membranes are used, consisting of sheets of fabric or paper hung from the ceiling or otherwise mounted with at least several inches displacement from the walls and having sufficient but low level of air flow to equilibrate the majority of the membrane to the internal air temperature. A GFCI-protected extension cord and powerstrip will be used to provide power to each tent.

The formula relied upon to obtain the ideal elevated temperatures is as follows, given as a lambda expression, which incorporates a first lambda (Python):

- $core2surf = \lambda core, air: core - (core-air)*0.191$

- $get_needed_room_air = \lambda air, febrile: core2surf(febrile, air) - ((98.6 - core2surf(febrile, air))/0.236)$

This gives us the needed heating temperature to get a desired change in body temperature, e.g. $get_needed_room_air(68, 100.4)$ returns 75.6F, meaning, in order to simulate a 100.4F core

temperature, a person must equilibrate to 75.6F air temperature before returning to receive a scan from the primary scanner located in 68F air temperature. This can be summarized more simply as, for every 1C (1.8F) elevation desired, the heated room must be that multiple of 4.23C (7.62F) above the scanning area's air temperature. Note, the exact coefficient was determined in a pilot study performed in June 2020, and may be refined by this study, which could alter the expected induced core temperatures.

Detailed Procedure - Blinded Temperature Study

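### The 0.48F ceiling on physiologic variability subtracts a core-scale SD from a surface-scale SD without the protocol's own 0.809 slope, so it is not an upper bound, and the SD, alpha and power behind the 28 participants are not stated

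*Combined protocol and SAP*

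**What the plan says.** All of the sizing argument is in section B, Population Size. It says that sample size depends on variability in the core-to-surface offset and that the design does not depend on person-to-person differences in core temperature. To estimate the offset variability, "we can extrapolate based on surface temperature data taken by the primary thermographic system obtained over the past six months". "This data shows a standard deviation of 1.11F", and this is taken to be "approximately the vector sum of variability in core temperature, measurement accuracy, and the physiologic variability". For the core term, "The variability in core body temperature has been found to be close to 1F"; the Introduction gives "a standard deviation of approximately 1F (0.6C" in brackets) for oral readings in healthy adults. The conclusion is a ceiling: "which would suggest the physiologic variability component is at most 0.48F, or half a degree".

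The target is "detecting elevated temperatures of 1.8F (100.4F threshold) to within 20" percent, explained as telling 100.40F from 100.04F in a one-sided paired t-test with the SD mentioned before. That is said to need 28 participants, with recruitment of up to 45. No alpha or power is given for this calculation.

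The relation between core and skin temperature is given later, under Controlled Temperature Rooms: surface equals "core - (core-air)*0.191".

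**The concern.** The two SDs being subtracted are on different scales. The 1.11F is described as the spread of skin temperatures, while the 1F is the spread of core temperatures. Under the protocol's formula a 1F difference in core produces only a 0.809F difference at the skin. Removing the core SD at full size takes out too much and leaves a residual that is too small. The contrast being sized, 100.40F against 100.04F, is on the core scale, so a skin-scale residual must also be divided by 0.809 before it is used.

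This matters because the result is presented as a ceiling. A reader would take 0.48F as the conservative input and the stated precision as safe. The paragraph's cautions (weaker environmental control, unknown core SD in the preliminary population) do not cover the mismatch, which remains even if the core SD is exactly 1F.

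**Working it through.** **Inputs from the documents.** Preliminary SD 1.11F, core SD about 1F, one-sided paired t-test, 28 and 45 participants (Population Size). Surface = core − 0.191 × (core − air) (Controlled Temperature Rooms). Effect 0.20 × 1.8F = 0.36F, which is 100.40F − 100.04F.

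**Assumed.** Alpha 0.05. Where 0.48F or 0.94F is used in the test, it is taken as the SD of the paired differences.

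**1. Reproduce the printed SD.** sqrt(1.11² − 1.00²) = sqrt(0.2321) = 0.482F. This matches 0.48F, so core variation entered with coefficient 1.

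**2. Apply the protocol's slope.** Surface = 0.809 × core + 0.191 × air. With a 1F core SD and air and measurement variance set to zero:
- at the skin: sqrt(1.11² − 0.809²) = sqrt(0.5776) = 0.760F
- on the core scale: 0.760 / 0.809 = 0.939F, which is 0.939 / 0.482 = 1.95 times the printed figure.

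**3. How far this depends on quantities the protocol does not give.** Core-scale residual = sqrt(1.11² − (0.809 × core SD)² − (0.191 × air SD)²) / 0.809.

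| Core SD (F) | Air SD, assumed (F) | Core-scale residual (F) |
|---|---|---|
| 1.0 | 0 | 0.94 |
| 1.0 | 1 | 0.91 |
| 1.0 | 2 | 0.81 |
| 1.0 | 3 | 0.62 |
| 1.0 | 3.4 | 0.49 |
| 0.9 | 0 | 1.04 |
| 0.8 | 0 | 1.11 |

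The air SD must reach about 3.4F before the residual returns to roughly 0.48F. A core SD below 1F pushes it above 0.94F. Even with unit slope, 0.48F is a ceiling only if the core SD is at least 1F: at 0.9F, sqrt(1.11² − 0.9²) = 0.65F.

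**4. Which SD gives 28?** Two routes reach it, and the text does not choose between them.
- *From 1.11F, no power term.* The smallest significant mean difference is t(0.95, n−1) × 1.11 / sqrt(n). At n = 27 it is 1.7056 × 1.11 / sqrt(27) = 0.364F; at n = 28 it is 1.7033 × 1.11 / sqrt(28) = 0.357F. So 28 is the first n to reach 0.36F under the stated test.
- *From 0.48F.* The stated test needs 13 at 80% power and 30 at 99%. It gives 28 only at an unusually high power of about 98–99%, or by leaving the stated test: a two-sided 0.05, 80% power normal approximation with SD of differences 0.48 × sqrt(2) gives 27.9, rounded up to 28.

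**5. Consequence on each route** (noncentral t, true difference 0.36F).

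| SD of differences (F) | Power, n = 28 | Power, n = 45 | n for 80% power |
|---|---|---|---|
| 0.482 | 98.6% | over 99% | 13 |
| 0.939 | 63% | 81% | 44 |
| 1.11 | 51% | 69% | 61 |

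At SD 0.939F and 80% power, 28 participants resolve 0.45F, and 0.45 / 1.8 = 25% of the elevation.

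**The case against.** The strongest objection is that 0.48F may have nothing to do with the 28. The only figure the paragraph labels a standard deviation is 1.11F, and the stated test gives 28 from it exactly if power is ignored. On that reading the slope never enters. This stands as far as it goes. Against it, the paragraph says core variability is irrelevant to the design, derives 0.48F for the offset, and moves straight from there to the sample size, so 0.48F is a natural reading too. The documents do not settle it, and neither route leaves the plan with a stated power.

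Second, the 1.11F may be core-corrected output. The Introduction says the system reports a core temperature estimate, and the remark in Population Size that no bias-to-normal algorithm was used fits that. Unit slope would then be consistent. The literal description is surface data, however, so either the number or the description needs correcting.

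Third, the paragraph hedges: it urges caution and offers only a reasonable error bound. Those hedges concern the environment and the unknown core SD, not the scale.

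A reader might go further and infer that the 20% precision is overstated about twofold, or that enrolment must rise by the variance ratio. The documents do not support this. It requires 0.48F to be the SD behind 28, the unstated implied power to be a standard the protocol set, and 0.94F to be an estimate when it is the value with air and measurement variance at zero. Nor do they support saying that even 45 participants are inadequate on the 0.94F figure, since 45 gives 81% power there.

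**Conclusion.** The concern holds in a limited form. If the preliminary data are surface temperatures, as written, 0.48F is not an upper bound on the protocol's own model. With a 1F core SD, the residual can be up to 0.76F at the skin or 0.94F on the core scale.

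The 0.94F should not be read as a worst case either. It rests on a core SD that the protocol says is unknown for that population, and it rises if that SD was below 1F. It falls if air temperature varied, which is plausible given the weaker environmental control.

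The effect on 28 is conditional. If 0.48F was used as the SD of differences, the plan's power for 0.36F could be as low as 63% at 28, and 44 participants, within the ceiling of 45, restore 80%. If 1.11F was used without a power term, the slope leaves 28 unchanged, but the study has about an even chance of detecting 0.36F at 28 and 69% at 45. All power figures assume one-sided alpha 0.05.

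**What to change.** In Population Size:

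1. Put both SDs on one scale. Preferably, convert each preliminary scan to the core scale with its logged air temperature, if that was kept, and recompute the SD; this also removes the air-temperature component.
2. Replace the 0.48F ceiling with the result. If conversion is not possible, say that the physiologic SD could be up to about 0.94F on the core scale (0.76F at the skin), assuming a 1F core SD, and do not call it a worst case.
3. If the 1.11F was already core-corrected output, correct the description of the data instead and keep 0.48F, stated as conditional on a 1F core SD.
4. State the SD, alpha and power that give 28, and whether the SD is that of the paired differences. Restate the resolvable difference at 28 and at 45 from those inputs.

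The cost is a recalculation and a few sentences. Enrolment can stay as planned. The downside is that the stated precision becomes less favourable, unless the 1.11F proves to be core-corrected and 0.48F is confirmed as the SD behind the 28.

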transparent to visible light. Also note the subject's left inner canthus is delineated on the image to the left with white specks (the hottest subset of pixels is replaced by white to provide feedback on device operation). The inner canthus is not the eye nor the tear duct, but rather a space on the nasal bridge midway between the eye and the nasion, very close to where eyeglasses with metal wire bridges terminating in a flat soft pad would contact the nasal bridge.

The overall goal of this study is to improve the IR thermometry science by 1) contributing a method for the objective manipulation of face temperatures using environmental air temperature changes and 2) developing a schema to use this method to assess the real-world sensitivity and specificity of non-contact IR core temperature measurement systems in normal, mild, moderate and severe fever groups, corresponding to core temperatures below 38C (100.4F), 38-39C (100.4-102.2F), 39-40C (102.2-104F) and above 40C (104F). This study is relevant for public health risk, because at present, there is no real-world objective test for thermographic febrile temperature screening devices, which significantly hampers the ability of regulatory authorities to identify improperly operating devices. A secondary goal is to determine the impact of potential confounds on non-contact thermographic temperature measurement. This translates to clinical utility, as any confounds could influence the decisions to prioritize the use of such systems. This is also related to public health risk, because the non-contact core body measurement systems the public is now relying on may have unacceptable biases in their determination of core temperature and it is possible they may even induce harm by altering behavior. Additional documentation is provided as a supplement for the review of this study detailing methods for the evaluation of thermographic systems.

B. Research Design and Methods

Study Population

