- NFC identification: the data collected will not be associated with any identifying information, instead being collected on a single printed sheet of paper having a near-field communication (NFC) sticker placed upon it. This NFC sticker will be used to activate the scanner as well as indicate which room a participant is equilibrating within. This is intended to reduce data collection errors as well as to reduce the possibility of personally identifiable information being exposed.
- Temperature measurements: Study participants will undergo non-contact body temperature measurements from several devices as well as an oral thermometry measurement. The non-contact thermal imaging temperature measurements must be

acquired while any eyeglasses are removed and the eyes must remain visible to the thermal imaging system during each measurement. The participant may be seated or standing for the non-contact thermal imaging temperature measurement, and the distance between the measurement system and the participant may be anywhere between 0.45 and 1.5 meters (1.5 to 5 feet). Masks can be worn during thermal imaging without interfering with the measurement.

- Imaging temperature measurements with glasses: Study participants will be asked to try to bring personal sunglasses and/or eyeglasses with them to the study for use in collecting thermal images of their faces while wearing these. Occluding the inner canthus is generally considered a major confound to acquiring an accurate imaging temperature with thermal imaging, and this data will be used to assess the impact of various eyewear on the output.
- Associated data: the ambient air temperatures at the time of each scan, the distance to participant's face, internal system parameters and the thermographs used to measure the imaging-based core body temperature will be stored, associated with the NFC UUID scanned prior to a scan. These thermographs will be encrypted with the public portion of a private/public key pair, the private portion being stored only on a separate password-protected and filesystem-encrypted computer used for analysis of the images. The thermal imaging system's filesystem is also encrypted and protected by a device-specific 160-bit key that is not practically recoverable from the device. System access is restricted by an RSA key and the system's network is protected by an on-device firewall.

Inclusion Criteria

1. Age > 18.
2. Have received a clinical oral thermometry measurement in the past.

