Exclusion criteria

1. Contraindication to oral temperature measurement.
2. Inability to follow instructions.
3. Any diagnosis associated with abnormal core thermoregulation, e.g. autonomic dysfunction.
4. Obvious signs of tissue damage present in either inner canthus.
5. Facial artery abnormality if previously diagnosed.
6. Experienced discomfort while receiving most recent clinical oral thermometry measurement.

Study Procedures

After a detailed explanation of the study and its potential risks and benefits and informed consent will be obtained by the principal investigator or one of the co-investigators. Participants will then receive a single printed sheet containing places to enter the demographic and clinical information outlined above, as well as an NFC sticker uniquely linking the information on the sheet to all temperature measurements (Data Collection Sheet included in protocol materials).

The total time involved for participants will be approximately 120 minutes, with 100 minutes being spent in actual study procedures. The oral and thermal imaging evaluations will be performed in rooms identified as suitable for the purposes below. There are two separable phases to the study, the first (**blinded temperature phase**) involves isolated non-contact measurements and oral thermometry in a building-temperature room after spending ten minutes in each of three blinded elevated-temperature rooms and the second (**equilibration phase**) involves serial non-contact measurements of the inner canthi of seated participants over ten minutes and an oral thermometry measurement in one elevated temperature room and one reduced temperature room. All study procedures will be performed in groups sized no larger than allowed by St. Olaf College's COVID-19 restrictions on social distancing within the selected rooms. Participants will receive a \$20 gift card in compensation for their time and effort involved in participation in this study.

[figure not shown]
Oral Thermometry

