Each participant is given a random room letter provided by a display configured to output a letter randomly pulled from a uniform distribution of the room numbers A, B and C. The participant is to go to said room and locate the NFC scanner inside and scan their data collection form to obtain their **nfc-room-scan** (to be used in later identifying which temperature group their body is simulating). Once the participant has entered a room, the door to the room is closed and the participant is instructed to wait while remaining relatively still for ten minutes while avoiding touching their faces and avoiding stressful content (e.g. avoid browsing the internet). At the conclusion of the ten minutes, determined by study personnel, the door will be opened and the subjects will exit the room and walk to the scanning area to scan their data collection form to obtain their **nfc-temperature-scan** and receive three consecutive face scans. After these scans are complete, participants will proceed to additional thermographic face scanning equipment to receive additional scans within one minute of exiting the equilibration room. Study personnel will record the results of any additional equipment scans along with a unique number displayed on the primary thermographic system display at the conclusion of their primary temperature scan. Study personnel will then obtain an oral thermometry measurement. After all oral and IR thermometry measurements are complete, participants will proceed to the next blinded temperature room and the above process is repeated. This is repeated until all participants have received scans after spending ten minutes in all three blinded temperature rooms, at which point they proceed to one of the equilibration rooms, described below.

Detailed Procedure - Equilibration Study

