In a second analysis, the equilibration time constants will be evaluated for possible linear correlations with the demographic data, although it is possible the small sample size and variability will preclude the detection of any significant correlations. In case there are nonlinear relations, scatter plots will be examined to determine if a low-order polynomial or other reasonable fit could explain a relation, while keeping in mind the fact each additional test is a multiple comparison, thus increasing the required p-value multiplicatively. Scatter-plots, trends and r-values will be reported, and this data may be collated with future collections of independent datasets.

The controlled face temperature data will be analyzed for sensitivity and specificity of each non-contact system used, first in a blinded analysis and then in an open-label analysis. First, the blinded face temperature data will be used to assign each recorded datapoint into normal, mild and moderate and severe fever groups, corresponding to below 38C (100.4F), 38-39C (100.4-102.2F), 39-40C (102.2-104F) and above 40C (104F). Note, the heated rooms' air temperatures were selected to produce simulated core temperatures that straddle the mild and moderate thresholds (hence, a well-performing system should place 50% of the measurements above the threshold and 50% below while a system relying on a bias-to-normal method might place only 10% above the selected threshold), therefore the severe fevers group

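### Blinded phase: nothing in the visible text requires eyewear to be off during the ten minutes in Rooms A–C, although the fever label assumes an inner canthus fully exposed to the room

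*Combined protocol and SAP*

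**What the plan says.** All references are to the combined protocol and SAP.

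- **Eligibility (B, Inclusion and Exclusion Criteria).** Eyewear is not an exclusion. The only criterion about the site itself is "Obvious signs of tissue damage present in either inner canthus".
- **Removal rule (B, Data Collection, temperature measurements).** Non-contact imaging temperatures must be "acquired while any eyeglasses are removed and the eyes must remain visible to the thermal imaging system during each measurement".
- **Room exposure (B, Detailed Procedure - Blinded Temperature Study).** In each of Rooms A–C the participant is to "wait while remaining relatively still for ten minutes while avoiding touching their faces" and to avoid stressful content. Eyewear is not mentioned.
- **Measured site (A, Introduction).** The inner canthus is described as "very close to where eyeglasses with metal wire bridges terminating in a flat soft pad would contact the nasal bridge". The same section says that glass and plastic do not transmit thermal light.
- **Label (D, Analyses).** The simulated core temperature is computed from the room's air temperature minus the scanner area's air temperature. It has no term for covered skin.
- **Eyewear-on images (B, Data Collection, imaging with glasses).** Participants are asked to bring glasses or sunglasses "for use in collecting thermal images of their faces while wearing these". The plan states that "Occluding the inner canthus is generally considered a major confound to acquiring an accurate imaging temperature with thermal imaging" and that "this data will be used to assess the impact of various eyewear on the output". It gives these images no time slot, and the list of data stored per scan has no eyewear field.

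**The concern.** The blinded phase uses room air to set the temperature of the canthus, then scores each device against a label derived from that air temperature. The label is right only if the canthus has equilibrated with the room. A participant who follows the written instructions can keep glasses on for the full ten minutes and take them off only at the scanner. Pads and lenses next to the measured site may change its exchange with the room's air and radiant surfaces. The protocol itself treats radiant exposure as important: it adds radiating membranes inside the tents (Controlled Temperature Rooms).

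At stake is the study's main comparison. D. Analyses expects a well-performing system to place 50% of readings above a threshold that the heated room straddles, and suggests that a bias-to-normal system might place only 10% there. If wearers' canthi are not where the label says, these fractions move for reasons unrelated to the device. Eyewear status is not listed as recorded, so the shift could not readily be separated from device behaviour.

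**Working it through.** **Inputs from the documents.** Core 98.6F; scanner area 68F; Rooms A, B and C at 68, 75.6 and 83.2F; surface = core − 0.191 × (core − air); room/skin coefficient 0.236 (all Controlled Temperature Rooms). SD 0.48F for the physiologic component and 1.11F for the preliminary total (Population Size).

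**Assumed.** The shielding fraction s. The documents give no value; 20% is used for illustration, with 50% as a wider case. The share of wearers is also not given, so the results below are for wearers only.

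**1. Reproduce the plan's calibration.**
- For a 100.4F core at 68F, surface = 100.4 − 0.191 × 32.4 = 94.21F. Needed room = 94.21 − (98.6 − 94.21)/0.236 = 75.62F, against 75.6F stated.
- For 102.2F the same steps give 83.24F, against 83.2F stated.
- In reverse, reading = (surface − 0.191 × 68)/0.809. With no shielding, Rooms A, B and C give 98.60, 100.39 and 102.19F. The calibration holds, and it presumes a canthus fully equilibrated to room air.

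**2. Model 1, lost rise.** A fraction s of the room-induced rise does not reach the canthus: reading = 98.6 + (1 − s) × design rise, with design rises of 0, 1.8 and 3.6F.
- s = 20%: 98.6; 98.6 + 1.44 = 100.04; 98.6 + 2.88 = 101.48F.
- s = 50%: 98.6, 99.5 and 100.4F.

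**3. Model 2, reduced heat loss.** In the protocol's formula, bare skin is at 92.8, 94.2 and 95.7F in Rooms A, B and C, warmer than the air in every room. A layer that weakens exchange with the room then keeps heat in. Replace 0.191 by 0.191 × (1 − s) in the room and convert back with 0.191 at the 68F scanner, glasses off.
- s = 20% (coefficient 0.1528): surfaces 93.92, 95.09 and 96.25F; readings 100.04, 101.48 and 102.92F.
- s = 50% (coefficient 0.0955): readings 102.2, 103.1 and 104.0F.

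**4. Compare at s = 20%.**

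| | Room A | Room B | Room C | C − A |
|---|---|---|---|---|
| Label | 98.6 | 100.4 | 102.2 | 3.6 |
| Model 1 | 98.6 | 100.0 | 101.5 | 2.9 |
| Model 2 | 100.0 | 101.5 | 102.9 | 2.9 |

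The two models disagree on sign. They agree that the between-room contrast falls by the fraction s.

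**5. Effect on classification of wearers at s = 20%.** Share above threshold = 1 − Φ((threshold − mean)/SD), shown for SD 0.48F / 1.11F.

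| | Room A above 100.4F | Room B above 100.4F | Room C above 102.2F |
|---|---|---|---|
| No shielding | <0.1% / 5% | 50% / 50% | 50% / 50% |
| Model 1 | <0.1% / 5% | 23% / 37% | 7% / 26% |
| Model 2 | 23% / 37% | 99% / 83% | 93% / 74% |

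For example, Model 1 in Room B at SD 0.48F: (100.4 − 100.04)/0.48 = 0.75, giving 23%. Model 2 in Room A: (100.4 − 100.045)/0.48 = 0.74, also 23%. Model 1 mimics bias-to-normal; Model 2 produces false positives in the unheated room.

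**The case against.** **The gap is inferred from silence.** The data collection sheet, study schema and sequencing spreadsheet are not available here and may contain an eyewear instruction. The protocol also places the canthus near the pad contact point; it does not say that glasses cover it. This stands as a limit on certainty. It does not close the gap, because the procedure section lists what participants must do during the ten minutes and leaves eyewear out.

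**The bias has no established direction.** A reader might infer that shielded wearers must read low in the heated rooms, so that they count as missed fevers and sensitivity falls. The documents do not support this. That result needs the shielded skin to keep part of its 68F-room temperature, whereas the protocol's heat-loss formula gives the opposite sign. Pad contact and skin cooling after removal are also undocumented. This objection stands in full: no direction is claimed.

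**Eyewear-on images are not said to be scored.** A reader might infer that they are, because one NFC sticker links all of a participant's measurements and "the blinded face temperature data will be used to assign each recorded datapoint into normal, mild and moderate and severe fever groups". But that sentence concerns the blinded-phase data, and the label rule matches the scan defined as following exit from a blinded room. Eyewear is barred from temperature measurements, and the eyewear-on images have their own stated purpose. What is missing is a flag and a rule to keep them apart. Stored thermographs might allow later sorting on the primary system; nothing promises this for secondary devices logged by hand.

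**Rooms D and E are already covered.** Participants there are imaged throughout the ten minutes, so the removal rule applies to the whole exposure. This stands.

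**Conclusion.** The point holds for the blinded temperature phase. The visible text lets an eligible wearer keep glasses on during the exposure that defines the label, at a site beside the nose pads, and the label cannot reflect this.

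The sign and size are not determined by the documents. At an assumed 20% shielding, wearers' mean readings miss their labels by 0 to −0.7F under one model and by about +0.7 to +1.4F under the other. For comparison, Population Size sizes the study on a 0.36F difference (100.40 versus 100.04F). The shrinkage of the room contrast is common to both models, and either sensitivity or specificity can be distorted. The effect on the whole sample scales with the share of wearers, which is unknown, and would be nil if glasses do not alter canthus equilibration.

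This is a cheap improvement to the procedure that removes a possible artefact. It is not a demonstrated bias of known direction, and it is not a finding that occluded scans enter the sensitivity count.

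**What to change.** **Main change.** In Detailed Procedure - Blinded Temperature Study, state that eyewear is removed on entering each of Rooms A–C and kept off through the last scored scan on the primary and secondary systems. The cost is one sentence and minor inconvenience to participants who need their glasses during the wait.

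**Safeguard.** Take eyewear-on images only after the scored scans, under a distinct code on every device, including the manual logs. Add one sentence to D. Analyses keeping them out of sensitivity, specificity and group means. The plan does not say that these images are scored, so this is a precaution and not the correction of an error.

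No change is needed for Rooms D and E.
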